11 REPORT OF ADVERSE EVENTS

The clinical evaluation of the subjects and safety of the multidisciplinary treatment is not the purpose of this study. Patients will only be visited before and after treatment. Therefore, no intermediate control will be performed to assess the safety and tolerability of the multidisciplinary anti-cellulite treatment during its application.

However, if patients report any adverse effects to the anti-cellulite treatment, the doctor will record it in the Data Collection Notebook, specifying:

- Type of reaction

- Intensity: mild (no limitation of daily living activities, patient may have mild discomfort), moderate (cause some limitation of daily living activities, patient may experience increased discomfort), severe (inability to perform daily living activities; patient may report intolerable pain or discomfort).
- Duration
- Causality with the DHA dietary supplement treatment under study: definitive, likely, possible, unlikely, unrelated, unknown.
- Therapy administered
- Resolution

If a subject reports a serious adverse event (see sidebar) during the time of this study, the physician should gather all available data and report them immediately (if possible within 24h.) by fax, telephone or e-mail to the Sponsor, who will implement the established Pharmacovigilance procedures in accordance with current legislation.

SERIOUS ADVERSE REACTION: is any adverse reaction that can be classified in one or more of the following categories:

- Lethal
- Life threatening
- It causes significant or persistent incapacity/ disability
- It causes hospitalization or prolongs hospitalization

Congenital anomalies/birth defects and serious adverse clinical consequences associated with use under conditions other than those set out in the Summary of Product Characteristics (SPC), overdose or abuse are also included.

Medical judgment should be applied when deciding whether an event or reaction is serious in other situations. Major adverse reactions or events that do not pose immediate threat to life, or do not cause death or hospitalization but may endanger the patient, should be deemed serious.

Sponsor:

[name]
PronoKal Group Medical Director
[name]
[name]
[contact]
[contact]

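### Section 11 ties prompt reporting to a serious adverse event but defines only a serious adverse reaction, so events not attributed to the program may go unrecorded or unreported

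*Combined protocol and SAP*

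**What the plan says.** Section 11 contains five statements that bear on capture of adverse events.

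- Recording: "if patients report any adverse effects to the anti-cellulite treatment, the doctor will record it in the Data Collection Notebook".
- Reporting: "If a subject reports a serious adverse event (see sidebar) during the time of this study", the physician gathers the available data and must "report them immediately (if possible within 24h.) by fax, telephone or e-mail to the Sponsor".
- Definition, in the sidebar that the reporting sentence points to: "SERIOUS ADVERSE REACTION: is any adverse reaction that can be classified in one or more of the following categories". Four outcomes follow: death, threat to life, lasting or significant disability, and new or prolonged hospital stay. Congenital anomalies are added, as are consequences of use outside a Summary of Product Characteristics (SPC), overdose or abuse.
- Closing text: "Medical judgment should be applied when deciding whether an event or reaction is serious in other situations", and "Major adverse reactions or events that do not pose immediate threat to life, or do not cause death or hospitalization but may endanger the patient" are to count as serious.
- Causality item on the record: "Causality with the DHA dietary supplement treatment under study: definitive, likely, possible, unlikely, unrelated, unknown".

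The same section says that safety is not what the study sets out to assess and that no check is made during treatment. Section 9.2.2 allows two visits only, before and after the program, and section 13.1 excludes clinical follow-up by the investigator in between.

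**The concern.** An adverse event is something untoward that happens to a participant. An adverse reaction is such an event already ascribed to the treatment. The reporting duty uses the first term and takes its meaning from a definition of the second, and the recording duty is also framed around effects of the treatment. A physician who follows the text to the letter could conclude that attribution comes first and that an unattributed event needs neither a notebook entry nor a message to the sponsor.

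This matters more here than in a trial with frequent visits. Treatment runs from 61 to 110 days (section 8), is managed outside the study, and is bracketed by two visits. Capture rests on what the woman reports, so the wording of the capture rule does much of the work. There is no control group (section 6.3), so an event left out because someone thought it unrelated cannot be reconsidered by comparing arms. If it is never recorded, the sponsor cannot reassess it. Section 10.1 plans descriptive statistics for every notebook variable, so any table of adverse effects would carry the same filter.

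As an illustration, a woman might be admitted with gallstones or an electrolyte disturbance and think it has nothing to do with the program. Section 7.3 lists both among the contraindications to the ketogenic diet. It does not say that the program causes them, but the sponsor would reasonably want to judge such a case itself.

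**Working it through.** The documents give no adverse event rate or other figure on this point, so there is nothing to reproduce or compute. The check is to set the sentences of section 11 side by side and follow typical cases through them.

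**Terms used**

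| Sentence | Term | Does it carry attribution? |
|---|---|---|
| Notebook rule | adverse effects of the treatment | Yes, by wording; the patient's report is the trigger |
| Reporting rule | serious adverse event | No, but it defers to the sidebar |
| Sidebar | serious adverse reaction | Yes, by the term |
| Closing text | event or reaction; reactions or events | No |
| Causality item | six grades, three of them unlikely, unrelated and unknown | No; causality is something to rate |

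The term serious adverse event is not separately defined in section 11. One further oddity follows from the table: the four listed outcomes are attached to reactions only, while the residual category of lesser but endangering situations names events as well. On the letter, an unattributed hospital admission is less clearly covered than an unattributed event of lower severity.

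**Cases**

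1. The woman attributes a complaint to the program and tells the physician. The notebook rule applies. The physician then rates causality and may choose any grade in the list "definitive, likely, possible, unlikely, unrelated, unknown". All six grades remain usable.
2. She tells the physician of a serious event but does not attribute it to the program, and the physician agrees. The notebook rule, read literally, does not cover it. The reporting rule covers it if the word event governs, and does not if the sidebar governs. The outcome depends on the reader.
3. She tells the physician of a non-serious event that she does not attribute to the program. The notebook rule, read literally, does not cover it, and no other sentence in the section does.
4. She does not mention the event. Nothing is captured under any wording that depends on patient report.

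The inconsistency therefore bites in cases 2 and 3.

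**Related wording in the same section**

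The causality item names a DHA dietary supplement as the treatment under study. Section 8 describes diet, protein products, vitamin and trace element supplements, exercise and a cosmetic cream whose listed ingredients do not include DHA. As written, causality would be rated against something not listed in the program. The sidebar's SPC clause has a similar difficulty, because the protocol identifies no SPC for the program.

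**The case against.** The strongest answer is that the section, read as a whole, already means events. The operative reporting sentence says event and sets no causality condition. The closing text applies seriousness to events as well as reactions. The causality scale offers unlikely, unrelated and unknown, which makes little sense if causality was meant as an entry condition. No sentence tells the physician to judge causality before recording or reporting. All of this stands, and it limits the point to what may happen under a literal reading.

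A reader might go further and infer that unattributed serious events will go unreported, or that the three low causality grades can never be used. The documents support neither. The first ignores the word event in the reporting sentence. The second fails because the notebook rule is triggered by the patient's attribution and the grade is assigned by the doctor, who may disagree with her.

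Two other objections also stand in part. Safety is outside the study's stated purpose, and section 9.1 has no safety endpoint, so no efficacy result turns on this. However, section 11 still imposes a reporting duty, and a duty should be unambiguous about what it covers. Also, a wording change cannot capture an event that the woman never mentions. That is a limit of the fix, not a reason to keep conflicting terms.

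What the objection does not remove is the pointer. The reporting sentence sends the reader to the sidebar for its meaning, and the sidebar's definition is of reactions. Nor does the closing text widen the notebook rule.

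**Conclusion.** The point holds as an inconsistency of terms with a possible effect on capture. Events that neither the woman nor the physician attributes to the program may go unrecorded, and serious ones may go unreported, if section 11 is followed to the letter. The other wording in the section suggests that the sponsor meant causality to be rated afterwards and not used as a gate, so the correction carries out the apparent intent.

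Its size cannot be given as a rate, because the documents supply no expected number of events and any figure would be invented. It affects which events reach the notebook and the sponsor. It does not affect the ultrasound or photographic endpoints. Confidence is high that the terms do not match and only moderate that an event would be lost in practice, since that depends on how the physician reads the sidebar. The conclusion assumes that no instruction outside the supplied text, for example on the notebook page, already settles the meaning. It is worth correcting because the correction is cheap and the two-visit design leaves little else to catch an omitted event.

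**What to change.** Change the wording of section 11 and the matching notebook page as follows.

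1. Retitle the sidebar *Serious adverse event* and define it as any untoward medical occurrence, whether or not considered related to the program, that meets one of the listed outcomes. Keep the outcomes as they are.
2. Use that same term in the reporting sentence and in the sidebar.
3. Word the recording sentence as any adverse event reported by the patient, whether or not considered related to the program.
4. State that causality is rated after recording, on the existing six-grade scale, against the program described in section 8. Remove the reference to a DHA dietary supplement.
5. As a minor point, replace the SPC clause with use other than as described in section 8, keeping overdose and abuse.

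Treatment, visits, endpoints and analysis are unchanged. The cost is the text edit and a few additional unrelated events to record among 30 women.

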12 ETHICAL ISSUES

12.1 General considerations

This study will be conducted in accordance with current regulations, international accepted ethical standards of Good Clinical Practice (CPMP/ICH/135/95) and the principles established in the latest version of the Declaration of Helsinki.

12.2 Evaluation by an Authorized Clinical Research Ethics Committee

Prior to its initiation, this study will be submitted to the Clinical Research Ethics Committee (CREC) of the Foundation of Health Management of the Santa Creu i Sant Pau Hospital to obtain its approval.

12.3 Patient information and informed consent

The patient will be informed about the study issues for their knowledge and written informed consent will be requested for participation in the study (Attachments 2 and 3).

12.4 Data confidentiality

Patient's identity in the study forms and in the digital files of the ultrasound and photographic images will be coded. The investigating physician will maintain a separate confidential record linking the identification codes with the patients' names.

13 PRACTICAL CONSIDERATIONS

13.1 Workplan

The principal investigator will be in charge of including the patients referred to his office. Once the patient has read the Patient Information Sheet (Attachment 2) and confirmed their willingness to participate, the investigator will obtain the signature of the Informed Consent Form (Attachment 3) and must keep them with the rest of the documentation of every subject.

The doctor will record the data requested in the CRD and will perform the skin ultrasound and the taking of photographs. The ultrasound images will be saved digitally, identified by the patient and the visit code; and will be saved to be evaluated at the end of the study, blindly, by the principal investigator and by another evaluator separately. Similarly, the photographs will be saved in digital files identified with the patient and visit code. The latter will be recoded before evaluation by two independent evaluators to ensure the blindness of the patient and the visit in which the photographs were taken.

The investigator will not perform any clinical follow-up of the patients during the multidisciplinary medical treatment and will only visit the patients prior to and after the anti-cellulite program.

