6.4 Masking Techniques

Both the ultrasound images and the photographic images will be blindly assessed by two independent researchers, who will not know the identity of the patients evaluated.

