9.2.4 Procedure for the assessment of skin ultrasound

Ultrasound changes will be assessed at the end of the study. The ultrasound images will be saved with the patient and the visit code. At the end of the study, ultrasound changes will be assessed by two evaluators, independently and blindly. The final result will be the average between both evaluations.

The parameters to be controlled are:

- Dermis thickness
- Hypodermis thickness
- Total skin thickness
- Dermis echogenicity
- Assess presence of dermal edema
- Presence of nodules in areolar subcutaneous tissue

- Indented subcutaneous fascicles in the dermis (length: measured from the center of the base to the point of maximum indentation in dermis)
- Presence and quantity of perpendicular fibrous septa

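### The principal investigator, who includes the women, is one of two readers of the primary ultrasound endpoint, and no described procedure secures the blinding that section 6.4 promises

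*Combined protocol and SAP*

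**What the plan says.** **Masking (6.4).** Ultrasound and photographic images "will be blindly assessed by two independent researchers, who will not know the identity of the patients evaluated".

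**Ultrasound reading (9.2.4 and 13.1).** Section 9.2.4 has two evaluators reading independently and blindly at the end of the study, and takes the mean of the two as the result. On storage it says: "The ultrasound images will be saved with the patient and the visit code". Section 13.1 repeats this labelling and names one of the readers; the images "will be saved to be evaluated at the end of the study, blindly, by the principal investigator and by another evaluator separately".

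**Other roles.** Section 13.1 also says: "The principal investigator will be in charge of including the patients referred to his office". It adds that the investigator "will only visit the patients prior to and after the anti-cellulite program", and that the doctor performs the ultrasound and takes the photographs. Section 12.4 says: "The investigating physician will maintain a separate confidential record linking the identification codes with the patients' names".

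**Photographs (9.2.3 and 13.1).** These get a fresh code that hides both the woman and the visit. Section 13.1 puts it this way: "The latter will be recoded before evaluation by two independent evaluators to ensure the blindness of the patient and the visit". No matching step is described for ultrasound.

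**The concern.** The primary endpoint (9.1.1) is the length of the subcutaneous fascicles indenting the dermis, measured from the centre of the base to the deepest point. A reader has to choose both points, so the measurement leaves room for expectation. The study has no control group, so an expectation of improvement cannot cancel between arms; it goes straight into the before/after difference.

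Against that background, the plan gives half of the primary reading to the person who includes the women. It does not separate that person from the investigator who sees them at both visits, the doctor who scans them or the physician who keeps the code list. It also gives the stricter masking procedure to the secondary endpoint and describes none for the primary one.

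**Working it through.** **1. The two image types compared**

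| | Ultrasound (primary) | Photographs (secondary) |
|---|---|---|
| Readers | Principal investigator and one other (13.1) | Two independent evaluators (9.2.3, 13.1) |
| Label on stored file | Patient and visit code (9.2.4, 13.1) | Patient code (9.2.3); patient and visit code (13.1) |
| Recoding before reading | None described | By patient and visit (9.2.3, 13.1) |
| Blinding promised in 6.4 | To patient identity | To patient identity |
| Result | Mean of two readings (9.2.4) | Mean of two readings (9.2.3) |

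**2. What the text settles about the principal investigator**

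- Reads the ultrasound images: stated (13.1).
- Includes the women: stated (13.1).
- Sees them at both visits: stated for the investigator (13.1), with no one else distinguished.
- Performs the scans: not stated. 13.1 says the doctor and 9.2.2 says the dermatologist.
- Keeps the code list: not stated. 12.4 says the investigating physician.

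Nothing bars the principal investigator from the last two tasks.

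**3. Which knowledge creates the bias**

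To push a before/after difference in one direction, a reader must know which image is before and which is after. The woman's name alone does not reveal this. The list in 12.4 links codes to names and is not described as a key to visits. The visit code stored with the ultrasound file is the more direct route, and it applies to the second reader as well as to the principal investigator.

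**4. Weight of one reader**

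The reported change is (D1 + D2)/2, where D1 and D2 are the two readers' before/after differences. If reader 1 is shifted by d and reader 2 by 0, the bias is (d + 0)/2 = d/2. If both are shifted by d, the bias is (d + d)/2 = d.

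**5. Illustration of scale**

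The documents give no reader bias and no standard deviation, and the 30 women (7.4) rest on no calculation, so there is no plan figure to reproduce. Assumptions made here: no true change, 30 women analysed, a two-sided paired t-test at 0.05 (10.2 states neither pairing nor sidedness), and a constant shift b in units of the SD of the averaged change.

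The critical value is 2.045 on 29 degrees of freedom. The noncentrality is (b/2)√30 with one reader shifted and b√30 with both. For b = 0.4 and one reader, that is 0.2 × 5.477 = 1.095.

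| b | False-positive rate, one reader shifted | Both shifted |
|---|---|---|
| 0.2 | 8.3% | 18.5% |
| 0.4 | 18.5% | 56.3% |
| 0.6 | 35.5% | 88.8% |
| 0.8 | 56.3% | 98.8% |
| 1.0 | 75.4% | about 100% |

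The nominal rate is 5%. The table shows sensitivity to b; it does not estimate b.

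**The case against.** The strongest reply is that the plan does provide for masking. Sections 9.2.4 and 13.1 both call the ultrasound reading blind and separate, and 12.4 says identity in the image files is coded. Independence in 6.4 may mean only that the two readers work apart from each other, which the plan delivers. Reading is held until the end of the study, so recognising a scan from memory is speculative. A principal investigator as one of two readers in a 30-woman exploratory pilot in one department is an ordinary staffing choice. And if the visit code is the real route to bias, changing the reader treats the wrong problem.

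Much of this stands, and it rules out three stronger readings:

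- A reader might infer that half of every primary value is read unblinded. The documents do not support that: they say the reading is blind, and what they lack is the procedure.
- A reader might infer that the principal investigator personally makes the scans and holds the list. The text leaves both open.
- A reader might infer that replacing this one reader would cure the problem. It would not, because the visit code would remain on the files.

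What the reply does not answer is that 6.4 promises more than separate reading: it says the readers will not know whose images they assess. For a reader who includes the women, and whose files carry patient and visit codes, nothing described secures this. The sponsor has already written a suitable safeguard and applied it only to the photographs.

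**Conclusion.** The point holds as a gap in the masking procedure for the primary endpoint and as a tension between 6.4 and 13.1. The missing recoding is the larger part of it; the choice of the principal investigator as a reader adds to it.

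The size is d/2 for a shift d in one reader, and up to d if both readers are influenced by a visible visit code. The value of d cannot be obtained from the documents, so the false-positive rates above are illustrations under stated assumptions. The conclusion also assumes that the stored codes are visible at reading and that the visit code can be understood by the reader; the plan does not say otherwise. It makes no claim that unblinding will occur. Since the remedy costs little and most of it is already in the plan, this is a cheap improvement worth making and not a fatal flaw in a pilot.

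**What to change.** 1. In 9.2.4 and 13.1, apply to the ultrasound images the recoding by patient and visit already planned for the photographs. Name someone who is not a reader to do it and to keep the recoding key until all readings are locked. The list of names in 12.4 can stay where it is.
2. Where existing staff allow, use readers who did not include, visit or scan the women. The plan does not show that the photograph evaluators can read skin ultrasound, so this should not be assumed.
3. If the principal investigator stays a reader, report the primary change from the other reader alone beside the two-reader average.
4. Reconcile 6.4 with 13.1: say who reads, what independent means, and that blinding covers the visit as well as identity.

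The cost is a small recoding task, one extra table line and some protocol wording. The possible downside is a less experienced reader if the principal investigator steps aside. Sample size and significance level are unaffected.

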13.2 Monitoring

CROSSDATA (CRO) will carry out remote monitoring of all patients, with follow-up reports of all of the study visits. If necessary, there will be on-site monitoring visits at the center.

13.3 Financing the study

The Sponsor will be in charge of the study expenses.

13.4 Disseminating the study results

The overall data will be used by the whole project, not individually.

With the results obtained, we will issue the final study report, which will be deemed confidential.

With the overall data we will try to maximize the exploitation of the study results in the form of publications or reports in conferences, always mentioning the study.

